### Risks to the Subjects

#### Human subjects involvement, characteristics, and design

Our proposed study design is an open-label randomized, controlled study piloting the use of POC VL testing and targeted DRM testing among HIV-positive children on ART age 1-14 years over a 12-month period in high-volume HIV treatment facilities in Kisumu, Kenya. At each facility, eligible children will be randomized 1:1 to either receive the intervention testing, consisting of quarterly POC VL testing and targeted DRM testing, or standard-of-care (SOC) testing based on the existing Kenyan national guidelines. We will follow the viral outcomes up to 24 months after enrollment for each child and compare VL suppression rates, defined as VL <1000 copies/mL by the Kenyan national guidelines, among intervention vs. control arms.

**Aim 1** of this study aims to determine the impact of point of care (POC) VL on the proportion of children achieving viral suppression and time to viral suppression for those who are either initiating ART or not suppressed.

The target population for aim 1 of the study includes approximately 700 HIV-infected children and young adolescents aged 1-14 years on ART at one of the intervention sites supported by FACES. Children who are outside of this age range will be excluded. These children will be randomized 1:1 to intervention vs. control arms. Therefore, approximately 350 children will receive the intervention (POC VL and DRM testing) and another 350 will receive the current standard of care as recommended by the Kenyan Ministry of Health, including routine viral load monitoring through centralized laboratory testing and DRM testing only for those failing 2nd line ART.

We conservatively estimate that around 90% of HIV infected children and adolescents and their families will agree to participate in the intervention portion of the study. Our sample size takes into account the potential for as much as 10% attrition due to loss to follow up, transfers out, or death based on current retention rates within the FACES program for children. Therefore, even if we experience as much as 10% attrition, we will still have a sufficient number of participants to evaluate the impact of the interventions.

**Aim 2** will explore the impact of targeted HIV drug resistance mutation (DRM) testing and patterns of DRM among HIV-infected children on ART without viral suppression.

In this aim we will determine the impact of DRM testing of children with viral load  $\geq$  1000 copies/ml among the 350 children 1-14 years on ART randomized to the intervention arm only. Based on current viral suppression rates in children at FACES sites, we anticipate at least 35% of children will have one or more POC VL results of  $\geq$  1000 copies/ml during the first 12 months of study follow up. This translates to around 100 DRM tests which allows us to generate point estimates with reasonable confidence intervals to assess our outcomes for this pilot study.

**Aim 3** of this study aims to better understand how our POC VL intervention functions using qualitative research methods and estimate the costs and time and feasibility of implementing pediatric POC VL testing and DRM monitoring at scale.

## Sources of materials

Data for Aims 1&2 will be collected in the following manner:

As part of standard care at participating health facilities, a standardized Ministry of Health routine HIV encounter form is filled for each child at every clinic visit. This form will provide baseline demographic and clinical data on participants at intervention and non-intervention sites. Additionally, clinic registers which document laboratory testing and results, patient visits, and pharmacy refills will also be utilized. A standardized, electronic data collection tool will be used to capture supplemental study information for both intervention and control participants. Data will be abstracted from by trained research data clerks using direct data entry via tablets into REDCap. REDCap meets all required standards for protection of personal health information. Data collected from study activities, namely process and outcome data on POC VL and DRM testing, will also be captured into the REDCap-supported data collection forms.

Finally, because currently VL results from routine VL testing are erratically recorded on the routine HIV encounter form, and therefore not always available in patient charts or electronic medical records, we will supplement VL outcome information from the National AIDS and STI Control Programme (NASCOP) online VL database and facility laboratory VL log books.

Data for Aim 3: For **Aim 3a**, the interviewers will audio record the KIIs or FGDs with a digital recorder and take field notes. Later the audio files will be transcribed from the interviews in the language that the interviewer occurred in, and if different from English, then translate them to English. Quantitative surveys assessing learnability, efficiency, memorability, error recovery, and satisfaction will be captured either on paper or electronically and stored on REDCap. For **Aim 3b**, we will use standardized cost and time menus to collect site costs and times, including start-up costs, clinic space, human resources, supplies, VL test costs, and timing of client arrival at a facility and VL sample collection, processing, and return. When data are not available from our cohort, we will utilize data from population-based studies from Kenya and sub-Saharan Africa. Additional cost data may be obtained from health facilities, published government information on labor costs, and health economics literature.

Of note, prior to shipment of any samples outside of Kenya, permission from appropriate authorities and agencies will be pursued as is standard in such cases.

## Potential Risks

Potential risks to participants in this study include social risks involved if information about participants or their family members, specifically HIV status, or other personal details were to be disclosed outside of the research setting. In particular, children and caregivers might face serious social risks (disruption of family, discrimination, and/or physical harm) if their HIV status were to be disclosed without their consent. These risks could be posed if a) clinic staff do not maintain confidentiality, or b) laboratory specimens are not handled in a manner that maintains confidentiality. The proposed study approach considers these potential risks. Clinic staff including service providers, laboratory technicians and phlebotomists, are already trained on maintaining privacy and confidentiality for all patients and this will be reinforced during clinic-wide trainings pre-study initiation.

Neither POC viral load testing nor DRM testing are anticipated to pose significant additional risks to study participants outside of the risks they are exposed to regularly as part of routine HIV care. Phlebotomy required for POC VL testing and DRM testing is also required for routine lab and viral load monitoring already a part of HIV care in Kenya. However, this will be more frequent than routine lab monitoring. Participants may experience some additional pain and anxiety due to this. This risk will be minimized by utilizing trained study nurses with experience collecting blood in children. Children undergoing to POC VL and DRM testing may switch to 2nd or 3rd line more frequently than those at non-intervention sites. This may present a risk if they are not adherent to 2nd or 3rd line treatment as 3rd line and salvage regimen options are limited in Kenya. However, more frequent VL testing may help to identify these children sooner and intervene such that they are able to re-suppress on their 2nd line regimen. DRM will also inform if 3rd line treatment options are needed which will facilitate more rapid transition to 3rd line when needed.

The use of ART in children within this study will follow Kenya National ART guidelines. ART risks include potential medication side effects, induced viral resistance from poor adherence or long-term exposure to ART limiting future drug options, and the burden of initiating lifelong treatment at an early stage of disease. However, Kenyan ART guidelines have clear recommendations on side effect monitoring and management and our study is intended to reduce the potential for drug resistance. It is important to note that this study is not intended to evaluate the safety and efficacy of ART for children in Kenya but rather to explore interventions that will maximize virologic suppression and therefore health outcomes for children with HIV.

## Adequacy of protection against risks

### Recruitment and informed consent

**Aims 1&2:** Participants will be recruited at the study facilities during routine clinic visits. Caregivers accompanying HIV infected children 1-14 years of age receiving or initiating ART will be approached and invited to participate. Recruitment may occur as part of pre-clinic information sessions provided by trained study staff (e.g. study nurses), by clinic staff during care, or by study staff before or after routine visits. We will offer study site providers a small incentive for referring patients who are eligible and enroll in the study. There is currently precedence among other local studies to offer a small incentive for successful study referrals. Site providers have been educated on enrollment eligibility and will be directed to not coerce or otherwise influence study enrollment. If the caregiver expresses interest in participating in the study, they will be invited into a private room to conduct the informed consent process where study staff will confirm if the caregiver is a parent or legal guardian. Informed consent will be obtained from at least one parent, or from the primary caregiver if both parents are deceased. Informed consent will be obtained by a study staff, namely study nurses, in the local language preferred by the caregiver. Caregivers and children over 13 years of age will be invited to participate and will be given clear explanations that this is something separate from their child's regular care and that they have the option of refusing to participate in any part of the research without any effect on their or their child's routine care received at the facility.

As part of this informed consent process, caregivers will be informed of the purpose and methods of the study, interventions, procedures to protect the confidentiality of the information, their rights to withdraw from the study at any time, randomization procedures, the fact that their participation or non-participation will not affect the medical care/performance evaluation that they or their child receives at the study health facilities, and persons to contact if they have any questions about the study. They will be asked to sign an informed consent form, or if illiterate, to provide a thumbprint in the presence of a non-study staff witness (the standard practice used in our other Kenyan studies, as approved by the Kenyan IRB). Caregivers will receive a small transport and time reimbursement at enrollment of ~\$5 USD. This is similar to enrollment incentives being offered locally by other research studies. We do not feel this enrollment reimbursement will be coercive or unduly influence caregivers to enroll as it is in line with other research being conducted in the same setting. Transport reimbursement of ~\$5 USD will also be offered at the 12-month, and possibly 24-month, visits to incentivize return for collection of endpoint VL samples. The same transport reimbursement will also be offered during the observational phase of the project after a 12-month study visit for every 6-month visit up to 5 years, since blood collection may be required out of routine care visit or phlebotomy for our study monitoring of DRM.

Children age 13 and older will be given the opportunity to provide assent for participation in the study. They will be provided information at an age appropriate level and given the opportunity to assent or decline separate from their caregiver. For those children who are not aware of their HIV positive status, which will be ascertained by asking their caregivers first, we will provide a modified assent form which removes any mention of HIV or HIV-related terms. All study participants will be informed that they will be followed up for a minimum of 12 months and up to 24 months.

Families who do not wish to participate, will continue to receive standard HIV services within the facility.

**Aims 3:** We will use purposeful sampling to identify key informants for each subgroup of key informants (**Table 3**). We will purposefully sample Groups 1 and 2 from both the control and intervention arms, ensuring we are capturing a diversity of key informant characteristics such as caretakers of younger vs. older children, children with and without viral suppression, male vs. female informants, etc. Study staff will recruit these participants from our enrolled study sample. For Group 3, we will again use purposeful sampling to interview providers and other facility staff, such as pharmacists, medical supervisors, nurses in charge, etc., with the goal of ensuring we capture a breath of professionals within the health facilities. Study staff, including our study coordinator, will recruit these participants from the facilities where we are conducting our study. For Group 4, we will use a combination of snowball and purposeful sampling, relying on our community partners and those attending our community stakeholder meetings to help us generate our initial pool of key informants. Once a person agrees to interview, we will also ask that person to help us identify another 2-3 persons to consider for interviews. For the focus

groups, we will use purposeful sampling to identify participants from national and county levels. We will ensure we capture a diversity in perspectives including local county and national policy makers, NGO staff, and academics working in this field and country. Study staff, including the lead investigators, will recruit these participants from known community partners and stakeholders.

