## ABSTRACT

Among nearly 1 million HIV-infected children receiving antiretroviral treatment (ART), as many as 40% of those living in resource limited settings have not achieved virologic suppression. Kenya, a UNAIDS fast-track and PEPFAR priority country, has an estimated 98,000 children aged 0-14 years living with HIV. Virologic suppression is achieved by only 65% of Kenyan children on ART translating to only 38% of the final UNAIDS 90-90-90 goal for population-level viral suppression. Feasible, scalable and cost-effective approaches to maximizing durability of ART regimens and ensuring viral load (VL) suppression in HIV-infected children are urgently needed. The goal of this pilot study is to determine the feasibility and impact of point-of-care (POC) VL drug resistance mutation (DRM) testing to improve VL suppression in children on ART within a PEPFAR-funded HIV care and treatment program in Kenya.

The proposed research is a randomized, controlled study to pilot the use of POC VL and DRM testing in children aged 1-14 years on ART at sites with on-site access to GeneXpert® technology. Children enrolling at each site will be randomized 1:1 to intervention (POC VL and targeted DRM testing) vs. control (standard-of-care) arms and followed for up to 5 years. The proposed study will be conducted in PEPFAR-supported HIV treatment facilities in western Kenya, a PEPFAR priority country. This pilot study will evaluate two critical components related to viral suppression in children via: 1) POC VL testing (**Aim 1a**) and 2) targeted DRM testing (**Aim 2a**) among children on ART. Our primary outcome is the proportion of children achieving VL suppression 12 months after enrollment for each child, with two secondary outcomes: 1) VL suppression and DRM patterns up to 5 years and, 2) time to viral suppression in those children not suppressed or initiating ART. We will also validate HIV-1 POC VL testing against current in-country gold standard VL testing (**Aim 1b**) in order to eventually scale up POC technologies for VL testing at national levels. We will also validate HIV-1 POC DRM testing, also named OLA Simple, against current in-country gold standard, consensus sequencing, DRM testing (**Aim 2b**).

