## C. Study Design and Research Methods

### Overall Study Design

We propose an open-label randomized, controlled study to pilot the use of POC VL testing and targeted DRM testing among HIV-positive children on ART age 1-14 years over a 12-month period in high-volume HIV treatment facilities in Kisumu, Kenya. We have chosen the study facilities to leverage existing POC technologies, as they are already equipped with GeneXpert® IV systems. Currently, these GeneXpert® systems are primarily being used for tuberculosis management. While validated for HIV VL monitoring, the technology remains to be tested for optimal integration into routine HIV clinical care. At each facility, eligible children will be randomized 1:1 to either receive the intervention testing, consisting of

quarterly POC VL testing and targeted DRM testing, or standard-of-care (SOC) testing based on the existing Kenyan national guidelines. We will follow the viral outcomes up to 24 months after enrollment for each child and compare VL suppression rates, defined as VL <1000 copies/mL by the Kenyan national guidelines, among intervention vs. control arms, accounting for pre-intervention VL suppression rates (**Figure 4**). Of note, after the 12-month study visit, the study will enter an observational-only phase to

continue to monitor for viremia and DRMs, especially among children on DTG-containing ART. During this observational-only phase of the project, participants will continue to receive testing, treatment, and other procedures as part of routine care, according to the standard-of-care then; study staff will not be providing any interventions, but only collect blood samples and administer questionnaires every 6 months up to 5 years of follow-up.

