To further analyze emerging DRM for DTG, we will follow participants longitudinally after they reach the study primary endpoint (of 12 months after enrollment) and follow their routine care VL patterns while on DTG via an observational extension of this project for up to 5 years. If VL $>200$  copies/mL is detected by reviewing routine care records, study staff will contact the participant for either additional blood collection or permission to use any stored sample for next-generation sequencing (NGS) and phenotyping. All samples with VL  $\geq$ 200 copies/ml will be tested by NGS using the Illumina MiSeq platform using Primer ID in [name] lab at Seattle Children's Research Institute in Seattle, WA (the children's hospital affiliated with the University of Washington). This NGS method will allow for detection of low-frequency drug resistance mutations (minority variants), which may be present at baseline and/or at time of viremia. Sequences will be analyzed for HIV drug resistance mutations using the Stanford HIV drug resistance database (HIVdb) genotypic resistance interpretation system, and drug resistance mutations will be reported at detection thresholds of 1%, 2%, 5%, 10%, and 20%. The results

will be returned to the facility staff. For phenotyping resistance patterns, [name] lab at the University of Washington will perform phenotypic resistance testing for those samples with relevant genotypic mutations. His lab requires two 2-mL cryovials of plasma, which will be collected at the time of blood collection for NGS sample collection. Neither validated NGS nor phenotypic resistance testing is currently available in Kenya, thus, requiring shipment of samples to the U.S. During this observational-only phase of the project, participants will continue to receive testing, treatment, and other procedures as part of routine care, according to the standard-of-care then; study staff will not be providing any interventions, but only collect blood samples and administer questionnaires every 6 months up to 5 years of follow-up. However, if any irregularities in routine care are noted in regards to treatment or monitoring by study staff during this observational-only phase, study staff will alert the health facilities for possible routine care interventions.

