## Procedures

**Blood sample collection:** For children in the intervention arm: blood samples will be collected every 3 months for POC VL testing and DRM testing per protocol for the first 12 months. For children in the control arm: blood samples will be collected per standard of care by non-study clinic staff per routine clinic schedule after study enrollment. Newly initiating children will undergo baseline VL and DRM testing as outlined above. After either intervention or control arm participants reach the primary endpoint of 12 months after enrollment, for the observational-only phase of this project, they may be followed every 6 months up to 5 years by routine clinic staff for VL monitoring; if VL $\geq$ 200, then study staff will request routine staff to share any leftover or stored plasma sample to obtain NGS genotyping and phenotyping. If no stored samples exist (for example, at the VL testing facility) or not in sufficient quantities, then the participant will be asked to return to the clinic for additional sample collection for NGS genotyping and phenotyping. Phlebotomy required for POC VL testing and DRM testing is also required for routine lab and viral load monitoring already a part of HIV care in Kenya. However, this will be more frequent than routine lab monitoring. Participants may experience some additional pain and anxiety due to this. This risk will be minimized by utilizing trained study nurses with experience collecting blood in children. Additionally, if the required 4ml of blood is not obtained, we will utilize dried blood spots which require less blood to reduce the need to perform additional phlebotomy. Once the testing for the study is completed, remaining samples will be stored in Kenya and later batch transported to the UW ICRC Laboratory Repository for storage for future studies.

**Blood sample storage and transfer:** Existing standards and best practices will be followed for blood sample storage and transfer. Greater details are found in the laboratory standard operating procedure.

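### The protocol contradicts itself on how long children are followed: its consent procedure gives at most 24 months, but visits and outcomes are planned to 5 years

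*Protocol*

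**What the plan says.** In the protocol, under Recruitment and informed consent (Adequacy of protection against risks), the instruction on duration is: "All study participants will be informed that they will be followed up for a minimum of 12 months and up to 24 months". The paragraph just before it offers transport reimbursement "during the observational phase of the project after a 12-month study visit for every 6-month visit up to 5 years", because blood may have to be drawn outside routine care.

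Elsewhere the protocol plans for 5 years:

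- The Abstract lists "two secondary outcomes: 1) VL suppression and DRM patterns up to 5 years". Specific Aims and Outcome Measure(s) also run to 5 years.
- Overall Study Design says that after month 12 study staff will provide no intervention but will "only collect blood samples and administer questionnaires every 6 months up to 5 years of follow-up". The HIV DRM testing text under Study methods repeats this.
- Study methods also describes follow-up of children on dolutegravir "via an observational extension of this project for up to 5 years".
- Procedures says of both arms that "they may be followed every 6 months up to 5 years by routine clinic staff for VL monitoring". If the viral load is 200 or more and no adequate stored plasma exists, "the participant will be asked to return to the clinic for additional sample collection for NGS genotyping and phenotyping".

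The 24-month limit also stands in Overall Study Design (in the same section as the 5-year plan), Study Timeline, Data analysis and interpretation, and Human subjects involvement. Study Timeline describes the whole study as lasting 2 years. The SAP's Study Design section follows viral outcomes only to 12 months.

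**The concern.** The duration of participation is one of the main things a caregiver weighs before agreeing. Here the only explicit duration that the protocol tells staff to give is shorter than the follow-up it plans. The later period is not passive: it includes questionnaires, possible extra blood draws in children, and shipment of samples to the United States for sequencing and phenotyping.

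Two pieces of work depend on months 24 to 60: the secondary outcome on suppression and resistance patterns to 5 years, and the monitoring of emerging dolutegravir resistance. If a family's consent covered only 24 months, the use of that child's later data and samples would be open to challenge.

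**Working it through.** The plan gives no figure to reproduce. The check is a comparison of stated durations, with arithmetic on months.

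**Inputs**

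| Input | Value | Source (protocol unless noted) |
|---|---|---|
| Duration participants are told | 12 to 24 months | Recruitment and informed consent |
| Longest planned follow-up | 5 years = 60 months | Overall Study Design; Study methods; Procedures; Recruitment and informed consent |
| Visit interval after month 12 | 6 months | Same sections |
| Expected enrolment | 90% of 700 = 630 | SAP, Power calculations |
| Attrition | about 10% in one year | Recruitment and randomization |

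**Months beyond the stated limit.** 60 − 24 = 36 months, and 36/60 = 60% of the longest planned follow-up.

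**Visits beyond the limit.** Six-monthly visits after month 12 fall at months 18, 24, 30, 36, 42, 48, 54 and 60, which makes 8. Those at months 18 and 24 fall inside the stated period, and the 6 from month 30 to month 60 fall outside it.

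**Child-visits beyond the limit.** The ceiling is 6 × 630 = 3,780, if every enrolled child attends every visit. If the 10% yearly attrition continued throughout (an assumption; the protocol gives it for one year), the number would be 630 × (0.9^2.5 + 0.9^3 + 0.9^3.5 + 0.9^4 + 0.9^4.5 + 0.9^5) = 630 × 4.058, or about 2,560. Both figures assume that all children enter the extension, whereas Procedures says only that they may be followed. The number of research blood draws cannot be derived. Overall Study Design and Study methods have blood collected every 6 months, while Procedures has routine staff monitor viral load and adds a draw only under stated conditions.

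**Which analyses fall where.** The 12-month primary outcome and the 24-month secondary comparison lie inside the stated period. The 5-year outcome and dolutegravir monitoring after month 24 lie outside it.

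**Does other text close the gap?**

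- Study methods has staff contact a participant with viremia for more blood or for permission to use a stored sample. This step follows a review of routine records, so follow-up is already under way. It is not consent to longer follow-up, visits or questionnaires.
- Human Subjects Protections requires separate ethical review of future studies or analyses. The extension is part of this protocol.
- Sources of materials requires permission from authorities before samples leave Kenya. That is not permission from families.
- The available protocol text describes no re-consent or re-assent step. Assent applies from age 13. A child enrolled at 8 to 12 could reach that age within 5 years, and no step covers this.

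**The case against.** The strongest objection is that the consent and assent forms were not available. They may state 5 years, or an extension consent may exist. The same section also says that caregivers are told the purpose and methods of the study, and the current methods include the observational phase. A reader might infer that families have not been told of the later visits, draws and sample uses, or that the later data were collected outside consent. The documents do not support that inference. They show instructions that conflict on duration, not an absence of disclosure.

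The spread of the 24-month figure across several sections also suggests wording left over from before an extension was added, rather than a deliberate limit on consent. The visit counts are ceilings, and the main inference of the trial is untouched.

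All of this stands, and it limits the consequence. It does not remove the conflict. The sentence is current protocol text and states what every participant is to be told. Under Protection against risk, explanations are to be given orally because some caregivers and adolescents may not be literate, so the duration that staff speak matters. If the forms say 5 years, the protocol disagrees with them. If they say 24 months, the extension lacks matching consent. Either way the sentence needs correction.

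**Conclusion.** The point holds as an internal contradiction on the length of follow-up that reaches into the consent procedure. If staff give the stated duration, up to 36 of 60 months and up to 6 of 8 observational visits lie beyond what families hear. This rests on the longest planned follow-up and on a six-monthly schedule kept to month 60.

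Only the extension is at stake. The conflict does not threaten the primary result. Whether any child was in fact enrolled under a 24-month limit cannot be settled from the protocol and SAP, so the need for re-consent is conditional on the forms used. The correction should be made because it is specific and cheap, and because the 5-year outcome depends on it.

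**What to change.** 1. Change the sentence under Recruitment and informed consent so that the stated maximum matches the planned follow-up. Have it describe the observational phase: six-monthly visits, possible extra blood draws, and sequencing and phenotyping abroad.
2. Reconcile the 24-month wording in Overall Study Design, Study Timeline, Data analysis and interpretation, and Human subjects involvement with the 5-year plan. Where 24 months is meant as an analysis time point, say so.
3. Reconcile Overall Study Design and Study methods (blood collected every 6 months) with Procedures (a conditional extra draw), so that families can be told what to expect.
4. State that any child enrolled under consent wording limited to 24 months is re-consented, and assented where the protocol's age rule applies, before study visits or sample use after month 24. If the forms already cover 5 years, the corrected sentence and a cross-reference to them are enough on this item.

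The cost is protocol wording and, only if the forms carried the 24-month limit, a consent step at a visit that is already planned.
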